### 6. STUDY PROCEDURES AND ASSESSMENTS

## 6.1. Informed Consent and Screening

#### 6.1.1. Informed Consent

The study visits will take place in a Clinical Evaluation Room (henceforth referred to as "study room") at Medline. The study personnel will obtain written informed consent from the participant either in the study room or over a video conference call with the participant. Written consent must be obtained from all participants and documented on an Informed Consent Form (ICF) that has received approval from an IRB/Ethics Committee. The signed ICF must be written in accordance with GCP and Good Documentation Practices (GDP) and must comply with all elements required by United States (US) Food and Drug Administration (FDA) 21 CFR 50.25 and International Conference on Harmonisation (ICH) 4.8, state and local regulations, and additional elements relevant to specific study situations (including a statement that Medline and relevant authorities have access to participant records). A copy of the signed consent will be given to each participant.

# 6.1.2 Verification and Eligibility

Following informed consent, the participants will undergo screening based on the inclusion/exclusion criteria detailed in Sections 5.1 and 5.2. Study personnel will verify participant eligibility in the study room at Medline, or over a video conference call with the participant. Thereafter, participants will receive a unique screening number that will be recorded in the Participant Screening Form (PSF). The reason for participant exclusion will also be documented in this form.

Potential participants who satisfy all inclusion/exclusion criteria for the study will be enrolled in the study and will be assigned a randomization sequence according to the Randomization Schedule. Participants will receive unique participant identification (ID) numbers based on the order in which they are enrolled after being screened. Demographic information of the participants will be documented in the PSF. Self-reported skin tone (or phototype) of the participants will be documented in the CRF. The Randomization Schedule, Case Report Forms (CRFs), PSF, and other study-related documents will be provided separately to the study personnel.

Medline Industries, LP
An evaluation of the skin protection characteristics of two commercially available skin barrier protectants
MED-2022-DIV71-003
08-AUG-2022

Version 2.0 CONFIDENTIAL Page 16 of 28

#### 6.1.3. Washout Period

Following study enrollment, participants will be instructed to adhere to a minimum 18 hours washout period, during which they must avoid application of any perfumes, or moisturizing, skin hydrating, or body cleansing products to both forearms and inner elbows. Participants will also be instructed to return for Visits 1 through 6 wearing clothing that allows exposure of their volar forearms and inner elbows.

#### 6.2. Visit 1

#### 6.2.1

Participants will be asked to self-report their skin phototype based on the Fitzpatrick skin phototype classification (scale I-VI), and the response will be documented in the CRF by the study personnel.

# 6.2.2 Randomization of Target Areas

Study personnel will confirm that the washout period of minimum 18 hours prior to Visit 1, has been successfully completed. Participants will wash their forearms and inner elbows with a standardized soap and use paper towels to dry each arm. After the participants' forearms and inner elbows are fully dried, they will be randomized according to the Randomization Schedule.

Figure 6.2.2. Randomization of Untreated Control Areas and Test Areas on the Volar Forearms and Inner Elbows

[figure not shown]

Figure 6.2.2. Key	
LL	Lower left
UL	Upper Left
LR	Lower Right
UR	Upper Right
LIE	Left Inner Elbow
RIE	Right Inner Elbow

Note: The inner elbow test areas will receive the same SBP as the one applied to the test area of the same arm

Medline Industries, LP

An evaluation of the skin protection characteristics of two commercially available skin barrier protectants MED-2022-DIV71-003

08-AUG-2022

Version 2.0 CONFIDENTIAL Page 17 of 28

Randomization will assign each participant to either Marathon® or Cavilon™ (designated SBP). The designated SBP will be applied to the volar forearm and inner elbow "test areas" of the participant's dominant arm, as determined by the participant. The other SBP will be applied to the volar forearm and inner elbow "test areas" of the participant's non-dominant arm. The SBP applied to the volar forearm and inner elbow test areas of a particular arm will be the same. Randomization will provide an equal probability for an SBP to be assigned to either the dominant or non-dominant arm. A distinct area on a particular volar forearm of the participant will be used as an "untreated control area" for the test areas on the same forearm.

# 6.2.3 Application of Skin Barrier Protectants (SBPs) and Corneometer® Measurements

Study personnel will draw 2-inch x 2-inch squares on the participants' forearms for each untreated control area and each test area using a non-toxic marker, such that three squares are marked on each volar forearm and inner elbow taken together. The lower squares on the volar forearms (LL and LR) will be marked about two inches above each wrist and will be used as untreated control areas. The upper squares on the volar forearms (UL and UR) will be used as test areas. The squares marked on the inner elbows of the participants (LIE and RIE) will be used as test areas as well. Refer to Figure 6.2.2 for details.

To measure baseline skin hydration, study personnel will use the Corneometer® to take the average of five measurements of skin capacitance and the standard deviation of the measurements for both the left and right forearm within each of the untreated control areas and volar forearm and inner elbow test areas. The Corneometer® measurements will be recorded in the CRF.

After the baseline measurements have been taken, study personnel will apply a thin layer of either Marathon ® or Cavilon TM (per the Randomization Schedule), such that the SBP covers the participants' skin within the border of the volar forearm and inner elbow test area squares. Each volar forearm will also include a 2-inch x 2-inch untreated control area square where no SBP will be applied. The participants will not be informed about the type of SBP applied to the volar forearm and inner elbow test areas. The participants will be instructed not to leave the study room, and that their forearms must remain exposed such that no article of clothing comes in contact with their forearms and inner elbows.

After the SBPs have been left to dry for at least one minute or have dried fully, Corneometer® measurements will be repeated in a manner similar to the baseline measurements, for each of the two untreated control areas and four test areas. The average of the Corneometer® measurements and the standard deviation of the measurements will be recorded in the CRF.

Participants will be dismissed from the study room and will be instructed to return the next day (within a  $24 \pm 4$  hours window) for Visit 2.

Medline Industries, LP
An evaluation of the skin protection characteristics of two commercially available skin barrier protectants
MED-2022-DIV71-003
08-AUG-2022

Version 2.0 CONFIDENTIAL Page 18 of 28

# 6.3. Visit 2 through 5

# 6.3.1 Corneometer® Measurements

The participants will return for daily visits except the weekend. For Visits 2 through 4, participants will be instructed to come to the study room within a  $24 \pm 4$  hours window from the previous day's visit.

During Visit 2 through Visit 5, the average of five Corneometer® measurements of skin capacitance and the standard deviation of the measurements will be taken for each of the untreated control areas and test areas on each volar forearm and inner elbow of the participants. The average of the Corneometer® measurements and the standard deviation of the measurements will be recorded in the CRF.

Note: During the period from Visits 1 through 6, participants will be allowed to bathe their arms using a standardized soap provided by the study personnel and will be asked to minimize scrubbing or any other abrasion of the treated skin. In addition, participants will be instructed not to engage in activities, for eg, sports (eg, tennis) or holding a baby that may cause significant abrasion on one arm and not the other.

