### 2.3. Risk/Benefit Profile

# 2.3.1.Potential Study Risks

This study entails minimum risk to the study participants. The SBPs used in the study are commercially available products that can be used in both home and clinical settings. There may be a minor risk of skin irritation for the participants. In such a case, for Marathon®, a clean tissue can be used before the film formed by the SBP dries. If the film has already dried, petroleum jelly can be used to soften the film, after which the SBP can be removed. In case of CavilonTM, the SBP can be removed using an adhesive remover containing hexamethyldisiloxane (HMDS). The risk to the study personnel is minimal, as they will use an applicator to apply the SBPs to the participants' volar forearms and inner elbows. The risk is further minimized as the study personnel will wear gloves during application of the SBPs.

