### 4. STUDY DESIGN

# 4.1. Overall Design

This is a randomized, single-blind study, which will evaluate and compare the duration of wear and durability of two commercially available SBPs, Marathon® and CavilonTM. The presence of the SBPs and their deterioration over time will be measured using a Corneometer®, which measures skin hydration.

During a washout period of minimum 18 hours prior to the first visit (Visit 1), participants will be asked to avoid application of cleansers, lotions, or perfumes to both forearms and inner elbows. During Visit 1, study personnel will confirm that the participants have successfully completed the washout period. Participants will then wash their forearms and inner elbows with a standardized soap and dry them using paper towels for each arm. After the participants' forearms and inner elbows have dried completely, study personnel will mark 2-inch x 2-inch squares with a non-toxic marker on the participants' volar forearms and inner elbows (starting about two inches above the

Medline Industries, LP

An evaluation of the skin protection characteristics of two commercially available skin barrier protectants MED-2022-DIV71-003

08-AUG-2022

Version 2.0 CONFIDENTIAL Page 13 of 28

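### The restriction on lotions and moisturizers is written only for the washout before Visit 1, so leave-on products may be used, unrecorded, while hydration readings are taken as a measure of film loss

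*Combined protocol and SAP*

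**What the plan says.** **Before Visit 1.** Section 6.1.3 instructs participants to observe a washout "during which they must avoid application of any perfumes, or moisturizing, skin hydrating, or body cleansing products to both forearms and inner elbows". Sections 1.1 and 4.1 give the same rule in terms of cleansers, lotions and perfumes. Section 4.1 then closes the period: "During Visit 1, study personnel will confirm that the participants have successfully completed the washout period". The Schedule of Activities (1.2) lists the washout under pre-visit activities only.

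**Visits 1 to 6.** The note in section 6.3.1 says that "participants will be allowed to bathe their arms using a standardized soap provided by the study personnel" and that they "will be asked to minimize scrubbing or any other abrasion of the treated skin". It also asks them to avoid activities that abrade one arm and not the other. The parallel text in 1.1 and 4.1 has the same content. None of the three mentions lotions, moisturizers or perfumes.

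**Measurement.** The Corneometer determines skin hydration through capacitance (1.1, 2.1). Treated skin is expected to read lower than untreated skin, and a rise is interpreted as the film breaking down (1.1; 4.1, Note 1).

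**Removal of the films.** Section 2.3.1 covers skin irritation. For Marathon it says: "If the film has already dried, petroleum jelly can be used to soften the film, after which the SBP can be removed". Cavilon, it says, "can be removed using an adhesive remover containing hexamethyldisiloxane".

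**The concern.** The plan protects the baseline reading from leave-on products but not the follow-up readings that form the primary endpoint. The documents do not say why the washout bars these products. Interference with a hydration reading is the natural explanation, but it is an inference.

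A participant who moisturizes the forearms on day 3, or over the weekend without visits, breaks no written instruction. Staff have no prompt to ask and no basis for logging a deviation. If the product raises the capacitance reading, the rise looks the same as loss of film. At the least this adds noise and apparent degradation within each product. If use or response differs between the two arms, some of it also enters the product comparison.

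**Working it through.** **1. Is there a restriction or a record after Visit 1?** The 6.1.3 rule names moisturizing and hydrating products and ties them to the washout. The 6.3.1 rule names soap, scrubbing, other abrasion and one-arm activities. The Schedule of Activities for Visits 2 to 6 lists Corneometer measurements, surveys, adverse-event monitoring and dismissal. The survey questions in 8.8.2 concern comfort, visibility, dirt and adherence to clothing. So no restriction on leave-on products and no item recording their use appears after Visit 1.

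**2. Do the control squares remove the effect?** Section 6.2.3 places the untreated squares (LL, LR) on the lower volar forearms. The inner-elbow squares (LIE, RIE) are both test areas. The degradation formula in 8.6, (C_o − C_t)/C_o, has no control term. Section 8.8.1 compares control readings between products alongside test readings but does not subtract them. The controls can therefore partly reveal lotion spread over a forearm, but the planned analysis does not correct for it. They also cannot show an effect that acts through a film.

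**3. How would use enter the results?** Let p be the share of participants using a product, and a and b the mean rise in reading on their Marathon and Cavilon test squares.
- Shift in mean apparent degradation: p·a for Marathon, p·b for Cavilon.
- Shift in the mean product difference: p·(a − b), which is zero when a = b.

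The documents give none of these values. As an assumed illustration, take p from 10% to 30% and a rise of 5 to 10 A.C.U.:
- Within a product: 0.10 × 5 = 0.5 to 0.30 × 10 = 3.0 A.C.U.
- In the product difference: 0 if the films respond alike, and 0.5 to 3.0 A.C.U. only in the extreme case where one film is affected and the other not at all. The direction is unknown.

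**4. Scale from the plan's own sample size (8.1).** Inputs are mean pair difference 17.5, margin 15, SD 5.05, alpha .0125, power 80%, N = 42. The noncentrality is (17.5 − 15)/5.05 × √42 = 3.21. The exact paired t-test, one-sided at .0125, gives power 0.807, and 42 is the smallest N that reaches 80%. The stated figure reproduces. (Two-sided at .0125 would need 49.)

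The same calculation with assumed disturbances, N = 42, one-sided .0125:

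| Assumed disturbance of the pair difference | Result |
|---|---|
| Mean shift −0.5 A.C.U. | power 0.60 |
| Mean shift −1 A.C.U. | power 0.35 |
| True difference 15, shift +0.5 | false-positive rate 0.053 (nominal 0.0125) |
| True difference 15, shift +1 | false-positive rate 0.16 |
| Extra SD 2: √(5.05² + 2²) = 5.43 | power 0.74 |
| Extra SD 3: √(5.05² + 3²) = 5.87 | power 0.67 |

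These rows apply only if something fails to cancel between arms, and only to the margin test used for sample size. Section 8.8.1 specifies between-product tests without stating the 15-unit margin.

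**The case against.** Four points can fairly be made on the other side.

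- **The soap permission may be a limited exception.** On this reading the washout rule continues and only cleansing with the supplied soap is allowed again. The wording does not carry that. It is a permission about bathing, the washout is confirmed as completed at Visit 1, and 6.1.3 shows that the authors name moisturizers when they mean to bar them. Instructions in separately supplied study documents cannot be seen, but the protocol should state the rule.
- **Pairing cancels equal effects.** Every participant wears both products, so moisturizer used alike on both arms, with a like response, leaves the mean product difference unchanged. This stands. It limits the core harm to noise and to apparent degradation within each product, unless use or response is unequal.
- **The untreated squares would show lotion use.** This stands in part, for the forearm only and without any planned correction.
- **Section 2.3.1 does not show a differential effect.** A reader might infer from it that emollients degrade Marathon more than Cavilon and so bias the comparison. The documents do not support that. The section names removal aids for use after irritation. It does not mention moisturizers, and it does not say that petroleum jelly leaves Cavilon unaffected. All that remains is that an unequal effect cannot be excluded.

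**Conclusion.** The gap is real and bears on the primary measurement. After Visit 1, leave-on products are neither barred nor recorded, and a rise in hydration is taken as film breakdown. Permitted use can therefore add noise and apparent degradation to the follow-up readings, and the planned analysis has no correction for it.

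Its size is unknown. The 0.5 to 3.0 A.C.U. shift in apparent degradation rests wholly on assumed usage and effect, and the corresponding shift in the product difference starts at zero. A reader might set the upper end against the 2.5 A.C.U. between the planned difference and the margin and conclude that the comparison is compromised. That would require one film to be affected and the other not at all, at the top of an assumed range, which the documents do not support. The point justifies a cheap correction. It does not show that the product comparison is biased.

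**What to change.** In the 6.3.1 note and the matching text of 1.1 and 4.1, extend the existing restriction through Visit 6: no perfume, moisturizing or skin-hydrating product, and no cleanser other than the supplied soap, on the forearms and inner elbows. Leave the safety provisions of 2.3.1 as they are.

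Add one yes/no CRF item at each visit asking about use since the last visit. Section 5.4 lets participation end for non-compliance and then replaces the participant, and 8.3 analyses only complete data. The amendment should therefore state that reported use alone is not a reason to withdraw or replace a participant. Keep the affected readings in the main analysis and add a sensitivity analysis without them.

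The cost is a minor amendment, one CRF item per visit, and a slight burden on participants for about one week. Sample size and randomization are unchanged.

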### 6.4. Visit 6 - Final Visit

# 6.4.1 Corneometer® Measurements

The study personnel will take the last set of the Corneometer® measurements (as detailed in Section 6.3.1) and record them in the CRF.

#### 6.5. Administration of Survey

Participants will complete surveys on Visits 1, 3, and 6, regarding their experience with the two SBPs.

# 6.6. Participant Dismissal

After completion of all study activities, participants will be dismissed from the study.

Note: Each participant will commence the study on Monday or Tuesday, which will permit daily readings for the first 72 hours, which is the more important window to evaluate SBP wear time. There will be a two-day break over the weekend, after which study personnel will take Corneometer® measurements either on Monday, or Monday and Tuesday, depending on the participant's start date.

Version 2.0 CONFIDENTIAL Page 19 of 28

# 7. ADVERSE DEVICE EVENTS (ADEs)

#### 7.1. Definition of ADE

Adverse event related to the use of an investigational medical device resulting from insufficiencies or inadequacies in the instructions for use, the deployment, installation, the operation, or any malfunction of the investigational medical device or from error in use.

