# 1.2. Schedule of Activities (SOA)

Assessments and Activities#	Pre-visit Activities	Visit 1	Visit 2–5	Visit 6 (Final visit)
Informed consent	X			
Participant Screening	X			
Demographics	X			
Participants complete minimum 18 hours washout period	X			
Participants wash forearms and inner elbows with standardized soap, and dry them using paper towels		X		
Participant forearms and inner elbows allowed to dry		X		
Randomization of SBP to be applied to the dominant arm of the participant §¥		X		
Baseline Corneometer® measurements taken		X		
SBPs applied at the volar forearm and inner elbow test areas according to the Randomization Schedule§		X		
SBPs allowed to dry		X		
Post-application Corneometer® measurements taken at untreated control areas and test areas		X	X	X
Participants complete surveys regarding experience with the SBPs ¥		X	X	X
Monitoring for adverse device events		X	X	X
Participant dismissal				X

# Study activities will occur after informed consent has been signed, and the participant has met all the inclusion criteria and none of the exclusion criteria.

08-AUG-2022

Version 2.0 CONFIDENTIAL Page 10 of 28

§ Randomization will assign each participant to either Marathon® or Cavilon™ (designated SBP). The designated SBP will be applied to the volar forearm and inner elbow test areas of the participants' dominant arm (as determined by the participant), whereas the other SBP will be applied to the volar forearm and inner elbow test areas of the participants' non-dominant arm.

\*The same type of SBP will be applied to the volar forearm and inner elbow test areas.

<sup>£Participants will complete surveys on Visits 1, 3, and 6.

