### 5.4 Early Withdrawal and Replacement

Participants will be discontinued or withdrawn from study participation at any time if either the participants or the study personnel feel that it is not in the participants' best interest to continue participation.

Participation in the study may end at several critical points:

Medline Industries, LP
An evaluation of the skin protection characteristics of two commercially available skin barrier protectants
MED-2022-DIV71-003
08-AUG-2022

Version 2.0 CONFIDENTIAL Page 15 of 28

- Participant withdraws from the study for any reason.
- Participant is not compliant with study procedures.
- Participant presents with adverse event(s) such that in the opinion of the PI it is in the best interest of the participant to discontinue study participation.
- Protocol violation requiring discontinuation of use of the study product(s).

Based on the above reasons, if any participant withdraws from the study or is dismissed, another participant will be recruited such that the total number of participants who complete the study will be 42. If a participant is being replaced, the randomization sequence associated with the replaced participant will be used for the new participant.

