#### 7.5. Relatedness of ADE and SADE

- Unrelated: This category applies to those ADEs, which after careful consideration, are clearly and incontrovertibly due to extraneous causes (disease, environment, etc.)
- Possible: This category applies to those ADEs for which, after careful medical consideration
  at the time they are evaluated, a connection with the Investigational Product administration
  appears unlikely but cannot be ruled out with certainty.
- Probable: This category applies to those ADEs, which after careful medical consideration at
  the time they are evaluated, are felt with a high degree of certainty to be related to the
  Investigational Product.
- **Definite:** This category applies to those ADEs, which after careful consideration, are clearly and incontrovertibly due to the Investigational Product.

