### 8.3. Populations for Analyses

The analyses will be performed on the intent to treat (ITT) population which consists of all participants who have complete data for all time points and have completed the survey for the secondary endpoint.

No per protocol, safety, or other analyses groups are planned.

Medline Industries, LP
An evaluation of the skin protection characteristics of two commercially available skin barrier protectants
MED-2022-DIV71-003
08-AUG-2022

Version 2.0 CONFIDENTIAL Page 22 of 28

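### Section 7.1, read literally, may leave out skin reactions to correct use, and no planned analysis covers adverse device events in everyone treated

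*Combined protocol and SAP*

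**What the plan says.** **Definition.** Section 7.1 requires an ADE to be related to use of the device, and then adds a cause: it must be one "resulting from insufficiencies or inadequacies in the instructions for use, the deployment, installation, the operation, or any malfunction of the investigational medical device", or stem from error in use.

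**Named risk.** Section 2.3.1 gives one risk to participants: "There may be a minor risk of skin irritation for the participants". It does not tie that risk to misuse or to a faulty product.

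**Collection.** The only safety row in the schedule (section 1.2) is "Monitoring for adverse device events", at Visits 1 to 6. Section 7.7 provides an ADE form and section 7.8 a form for serious and unanticipated events. No form or rule is given for other adverse events.

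**Grading.** Section 7.5 classifies ADEs on four levels. The lowest, Unrelated, is for events that "are clearly and incontrovertibly due to extraneous causes"; the highest, Definite, is for events due to the product itself. Section 7.6 judges expectedness against the risk information already described.

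**Analysis.** Section 8.3 defines one analysis set: participants with complete data at every time point and a completed survey. It adds: "No per protocol, safety, or other analyses groups are planned".

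**Replacement.** Section 5.4 lists an adverse event among the reasons for leaving, and says that "another participant will be recruited such that the total number of participants who complete the study will be 42". Section 8.2 likewise replaces anyone with incomplete data.

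**The concern.** There are two separate weaknesses, one in recording and one in reporting.

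In recording, the list of causes in 7.1 has no clear place for a reaction to a product that was applied as instructed and worked as intended. That is the ordinary way in which a skin protectant would irritate skin. Staff who follow 7.1 to the letter could leave such an event off the ADE form; staff who follow 7.5 and 7.6 would record it.

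In reporting, a participant who leaves because of a reaction is by construction outside the only analysis set and is replaced. Section 8.8 plans no table of ADEs in any population.

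At stake is a report with an incomplete account of tolerability, from a study that section 2.3.2 says may inform clinical use decisions. Recording also bears on oversight, because one ground for suspension in section 9.1.3 rests on review of ADEs.

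**Working it through.** **1. The definition against the sections that use it.**

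| Section | What it implies about irritation from correct use |
|---|---|
| 7.1 | An ADE only if it arises from inadequate instructions, deployment, installation or operation, or from malfunction or use error |
| 2.3.1 | A foreseen risk, with no such condition |
| 7.5 | Gradable up to Definite on causation by the product alone; the scale also allows an Unrelated level |
| 7.6 | Can be an expected ADE, since expectedness is set against the described risk |

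An event that 7.1 has already defined as related to use cannot be graded Unrelated. Possible, Probable and Definite remain usable. So 7.1 conflicts with one level of the scale, and is narrower than 7.5 and 7.6 assume.

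**2. Other routes by which a reaction could be captured.** A serious reaction not previously identified in nature, severity or incidence meets the definition in 7.3, which has no malfunction or error condition, and is recorded under 7.8. The gap is therefore limited to non-serious events. The survey (section 8.8.2) asks about comfort at Visit 1. At Visits 3 and 6 it asks about visibility, debris and sticking to clothing, not about irritation.

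**3. Who is analysed.** The 8.3 set contains completers only, and 5.4 and 8.2 refill it to 42. Section 8.7 promises that missing data will be quantified, but asks for no count by reason for leaving. Section 8.8 contains no ADE summary.

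**4. The plan's own figure.** Section 8.1 gives a margin of 15, a mean paired difference of 17.5, SD 5.05, alpha .0125 and 80% power. The standardised effect is (17.5 − 15)/5.05 = 0.495. With n = 42 the noncentrality is 0.495 × √42 = 3.21 on 41 degrees of freedom, and a one-sided test (sidedness is not stated) has power 0.807. So 42 reproduces. Nothing in this point changes it.

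**5. Illustration only.** The documents give no rate of irritation or withdrawal. Suppose a fraction r of treated participants leave for irritation, none of the 42 completers is affected, and events are tabulated in completers only. The number treated is 42/(1 − r), rounded up. Intervals are exact binomial 95%: lower limit Beta(0.025; x, n − x + 1), upper limit Beta(0.975; x + 1, n − x).

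| r | Treated | Leavers | All treated | Completers |
|---|---|---|---|---|
| 2% | 42/0.98 → 43 | 1 | 2.3% (0.06% to 12.3%) | 0/42 |
| 5% | 42/0.95 → 45 | 3 | 6.7% (1.4% to 18.3%) | 0/42 |
| 10% | 42/0.90 → 47 | 5 | 10.6% (3.5% to 23.1%) | 0/42 |

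For 0/42 the upper limit is 1 − 0.025^(1/42) = 8.4%, so the interval is 0% to 8.4% in every row.

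These proportions are per person. Each participant wears both products, one on each arm, so they say nothing about either product unless arm and site are recorded.

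**The case against.** The strongest reply is that the protocol, read as a whole, treats product reactions as ADEs. Section 7.1 opens with relation to use, and a reaction to applying a liquid film could be read as arising from deployment or operation. Section 7.5 grades up to causation by the product, 7.6 compares events with the described risks, and Grade 1 in 7.4 fits mild irritation. The ADE form in 7.7 is not restricted to the analysis set, so replacing a participant does not remove a completed form. The investigator reviews all ADEs under 9.1.2 whatever 8.3 says. The study is post-market, minimal-risk and has no safety objective.

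Much of this stands, and it rules out three stronger readings that a reader might infer:

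- *Irritation will go unrecorded.* Not supported: 7.5 and 7.6 point the other way, so the outcome depends on which section staff follow.
- *Participants who leave because of irritation are lost from the record.* Not supported: their ADE forms may exist and 8.7 quantifies missing data. What is absent is a planned analysis that includes them.
- *The relatedness scale cannot be applied at all.* Not supported: only its Unrelated level conflicts with 7.1.

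The reply does not remove the inconsistency. That 7.5 and 7.6 assume a broader definition than 7.1 states is the reason to correct 7.1. The lack of a safety objective also does not explain why treated participants should be missing from even a descriptive table.

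**Conclusion.** The point holds in limited form. Taken literally, 7.1 may exclude non-serious skin reactions to correct use, in conflict with 2.3.1, 7.5 and 7.6. Separately, no planned analysis includes events in replaced participants, and neither an ADE summary nor a tabulation of withdrawals by reason is specified.

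The size cannot be derived from the documents. The comparison of 3/45 with 0/42 rests on an assumed withdrawal rate, on no completer being affected and on tabulation in completers only. No section states that last rule; it would follow if the 8.3 set were used for every table. The illustration shows the direction of the possible error, not an expected amount. The sample size and the primary and secondary analyses are not affected.

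**What to change.** - **Section 7.1:** change *resulting from* to *including any event resulting from*. Reconcile the section with 7.5 and 7.6 so that any untoward skin event at a treated site is recorded with arm and site, and then graded for relatedness. Recording every adverse event whatever its location or cause would go further than this point requires.
- **Section 8.3:** replace the sentence that rules out a safety group with a descriptive safety set of everyone who had any study product applied, including replaced participants. Tabulate ADEs by product and site, and withdrawals by reason.

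The cost is slightly more event recording and one or two small tables. The target of 42 completers and the efficacy analyses do not change.
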